7.5.2 Analysis of Progression-Free Survival

The PFS analyses will be conducted using both the primary and the ITT definitions of PFS.

The PFS function for each treatment arm will be estimated using the KM product limit method and will be displayed graphically. A two-sided 95% CI for median PFS in each arm will be computed via the Brookmeyer Crowley method. Estimates for one-year and two-year PFS if last patient is followed for at least 1 or 2 years correspondingly, will be presented along with their associated 95% CIs. These estimates will be come from the KM curve and their standard errors (SEs), for use in constructing CIs, will be computed using Greenwood's formula²⁰.

The estimate of the PFS hazard ratio, of ELd to Ld, will be calculated using a Cox proportional hazards model, with stage of disease (ISS 1 – 2 versus 3) as the stratification factor and treatment

as the sole covariate. Ties will be handled using the Breslow method²¹²². A two-sided, 95% CI for the hazard ratio will also be presented.

A by-subject listing will be presented including treatment arm, PFS duration under the primary definition, PFS duration on the ITT definition, whether the subject was censored under the primary definition, and if censored, the reason, and whether the subject was censored under the ITT definition, and if censored, the reason.

7.5.3 Time to Tumor Response, and Duration of Response

The distributions of duration of response will be estimated, by arm, using the KM product limit method. The KM estimates will be presented graphically and tables will be produced presenting number of events, number of subjects involved, medians, and 95% CIs for the medians.

Time to tumor response, which does not involve censoring, will be summarized by treatment group, using descriptive statistics.

A by-subject listing will be presented including treatment arm, and, duration of response, whether the subject was censored for duration of response, and, if so, the reason.

7.5.4 Efficacy Laboratory Tests

A by subject listing of efficacy will be provided to present the following:

- Percent change in serum and urine M-protein, from baseline and nadir.
- Serum free light chain kappa and lambda concentrations and the kappa/lambda ratio.
- Serum and urine immunofixation test results.
- Corrected Calcium results
- Results of bone marrow analysis, including plasma cells (%) and clonality of plasma cells.
- Radiologic evaluation of extramedullary plasmacytoma and lytic bone lesions

7.6 Safety

Safety summaries will be based on the treated subject population, grouped by treatment regimen received. All subject's treatment regimen received will equal the arm to which they were assigned at randomization as long as they did not receive the wrong regimen at every administration.

7.6.1 Adverse Events

AEs will be categorized using the most recent version of the MedDRA, by system organ class (SOC) and preferred term (PT). The severity of AEs will be graded using the NCI CTCAE (v 3.0).

On-study AEs are defined as non-serious and serious AEs with an onset date on or after the first dose until 60 days after the last dose. See [Section 8.4, Imputing AE Onset Dates](#), for a discussion of imputation rules for incomplete or missing AE onset dates. If the relationship to study drug is missing, then the AE will be assumed to be related to study drug.

Unless specified otherwise, AEs will be counted only once within each SOC and PT, according to their worst CTC grade.

Tables will be sorted by SOC and PT, with SOC's ordered by decreasing frequency overall and then alphabetically. PTs will be sorted within SOC's by descending frequency overall and then alphabetically. The sorting will be done based on the total column when arms are presented side-by-side.

Frequency tables of the worst grade of on-study AE will be presented. One summary table will present AEs broken out by individual grade, 1, 2, 3, 4 or 5 along with an Any Grade category. Another one will present AEs by grouped grades as follows "Any, Grade 3-4 and Grade 5." The summary of combined grades will be repeated for on-study drug-related AEs.

A by-subject listing all AEs will be presented.

In addition the following will be presented by treatment arm:

- Frequency of AE before and after cycle 19 for subjects on the Elotuzumab arm
- Exposure-adjusted AE incidence rates (including multiple occurrences of unique events) will be calculated for each SOC and PT.

Exposure-adjusted incidence rate per 100 person-years will be used and will be calculated as:

$$100 \times \left(\frac{\text{Total number of unique AEs}}{\frac{\text{subject date of last dose of study drug} - \text{subject date of first dose of study drug} + 60 + 1}{365.25}} \right)$$

and will be displayed along with a count of events.

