4.5 Selection and Timing of Dose for Each Subject

4.5.1 Study Drug Administration

Dexamethasone

On weeks without elotuzumab (including the control arm), administer the weekly dose of 40 mg dexamethasone on Day 1, 8, 15, and 22 (-1 to +3 days). At the investigator's discretion, the oral dexamethasone may be given as a split dose over 2 consecutive days each week.

On weeks of elotuzumab infusion, administer dexamethasone as a split dose of:

- 28 mg po (between 3 - 24 hours prior to the start of elotuzumab infusion) AND
- 8 mg IV (on the day of elotuzumab infusion at least 45 min prior to the start of infusion).
- At the discretion of the investigator, the oral dexamethasone component may be given as a split dose 12 - 24 and 3 hours prior to elotuzumab.

Elotuzumab

Elotuzumab will be administered intravenously at a dose of 10 mg/kg weekly (Days 1, 8, 15, and 22 of a 4-week cycle) of the first 2 cycles and every 2 weeks (Day 1 and Day 15) for Cycles 3 through 18, then at a dose of 20 mg/kg every 4 weeks Cycle 19 (Day 1) and beyond. A window of -1 to +3 days is permitted in Cycles 1 and 2.

In Cycle 1 and 2, an elotuzumab dose that falls outside of the pre-specified window must be skipped.

In Cycles 3 and beyond, elotuzumab dosing may be delayed for up to 1 week as clinically indicated. The reason for the delay must be recorded on the CRF. If unable to administer within 1 week, then the dose should be skipped and resumption of the elotuzumab continues per the protocol defined schedule.

In addition, the following must also be administered 30 - 90 min prior to any elotuzumab:

- H1 blocker: diphenhydramine (25 - 50 mg po or IV) or equivalent
- H2 blocker: ranitidine (50 mg IV) or equivalent
- Acetaminophen (300 - 1000 mg po).

See [Appendix 3](#) for elotuzumab dosing instructions.

Lenalidomide

Lenalidomide will be taken orally 25 mg once daily for the first 3 weeks of a 4-week cycle. On the days of elotuzumab administration, the dose of lenalidomide is to be administered at least 2 hours after completion of elotuzumab dosing. Subjects should not break, chew or open the capsules.

Table 4.5.1-1: Treatment Schedule

Investigational Arm (ELd Arm)												
Cycle #	1 - 2				3 - 18				19 +			
Day # (-1/+3 days)^a	1	8	15	22	1	8	15	22	1	8	15	22
Dexamethasone - PO	28 mg	28 mg	28 mg	28 mg	28 mg	40 mg	28 mg	40 mg	28mg	40 mg	40 mg	40 mg
Dexamethasone - IV	8 mg	8 mg	8 mg	8 mg	8 mg	-	8 mg	-	8 mg	-	-	-

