2 STUDY DESCRIPTION

2.1 Study Design

This is a Phase 2, randomized, open-label, multi-center trial investigating lenalidomide/dexamethasone with and without elotuzumab in subjects with newly diagnosed, previously untreated multiple myeloma who are ineligible for high-dose therapy plus stem-cell transplantation (SCT) because of age (≥ 65 years) or coexisting conditions.

The primary objective of this study is to estimate the ORR of elotuzumab + lenalidomide/dexamethasone in subjects with newly diagnosed, previously untreated MM.

Eligible subjects will be randomized in a 1:1 ratio to receive either elotuzumab/lenalidomide/dexamethasone (ELd) [Investigational Arm] or lenalidomide/dexamethasone (Ld) [Control Arm]. The randomization will be stratified by International Staging System (ISS) stage (1 - 2 versus 3). Approximately eighty subjects in total will be randomized to either arm.

A cycle is defined as 28 days. Treatment with study drug continues until disease progression (PD), unacceptable toxicity or subject meets other criteria for discontinuation of study drug.

Disease assessments, based on the International Myeloma Working Group (IMWG) response criteria, will be conducted every 4 weeks relative to the first dose of study medication until disease progression. Response and progression assessment will be investigator-based and no central lab or independent review is planned.

For the subject who does not have documented disease progression at time of study drug discontinuation, tumor assessments should still be performed according to the same schedule until disease progression even if a subsequent anti-myeloma treatment is initiated prior to disease progression.

Blood samples for pharmacokinetic (PK) and immunogenicity analysis will be collected in all subjects who received elotuzumab, prior to elotuzumab infusion on Day 1 of Cycles 1 through 4, 6, 9, 12, 15 and 18, as well as at the end of the study or discontinuation of treatment, and 30-day and 60-day follow-up visits. In addition, serial PK samples including two hours post end of infusion will be drawn in Cycles 1, 2 and 3.

For full details of the schedule and timing of assessments see Protocol Section 5.

[REDACTED]

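### The adverse-event table split at Cycle 19 has no person-time by period and no stated denominator, so it can mislead in either direction when the event rate has not changed

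*SAP*

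**What the plan says.** SAP 7.6.1 lists, among its additional outputs, "Frequency of AE before and after cycle 19 for subjects on the Elotuzumab arm". The default counting rule in that section, unless stated otherwise, is that "AEs will be counted only once within each SOC and PT, according to their worst CTC grade". Nothing else is specified for this table: no denominator, no person-time, and no rule for which side Cycle 19 itself falls on.

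The next bullet reads "Exposure-adjusted AE incidence rates (including multiple occurrences of unique events) will be calculated for each SOC and PT". Its denominator runs from first to last dose of study drug plus 61 days, with no split at Cycle 19. AEs count as on-study if they have an "onset date on or after the first dose until 60 days after the last dose".

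The split coincides with a schedule change in Protocol 4.5.1, which gives elotuzumab "then at a dose of 20 mg/kg every 4 weeks Cycle 19 (Day 1) and beyond". SAP 2.1 states that "A cycle is defined as 28 days" and that "Treatment with study drug continues until disease progression (PD), unacceptable toxicity" or another discontinuation criterion is met.

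On timing, the SAP's schedule of analyses puts every planned analysis in the CSR, at a cut no sooner than six months after the final subject's first treatment, and allows later analyses. Protocol 8.3.2.2 says the study duration was expanded under amendment 03, without giving a length.

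**The concern.** A percentage of subjects with at least one event rises with time at risk. The two columns differ in time at risk and in who is in them: everyone treated with ELd enters the first, and only those who stayed on treatment for 18 cycles enter the second. A reader will naturally use the table to ask whether AEs changed when the elotuzumab schedule changed. The difference between columns could come entirely from follow-up length and selection, and the whole-treatment exposure-adjusted rates cannot separate these from a real change.

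Ascertainment also differs. In Protocol Table 5.1-3 the Day 15 AE assessment is dropped from Cycle 19.

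**Working it through.** The documents give no figure for this comparison, so there is none to reproduce. The checks below show what an unchanged event rate would produce.

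**1. Length of the first period.** 18 cycles × 28 days = 504 days = 504/365.25 = 1.38 years = 504/30.4375 = 16.56 months.

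**2. Same subject, constant rate.** P(at least one event) = 1 − exp(−rate × time). The rate is an assumption, shown at two values.

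| Period | Days | 25 per 100 person-years | 50 per 100 person-years |
|---|---|---|---|
| 18 cycles before | 504 | 1 − exp(−0.345) = 29.2% | 1 − exp(−0.690) = 49.8% |
| 6 cycles after | 168 | 1 − exp(−0.115) = 10.9% | 1 − exp(−0.230) = 20.5% |
| 12 cycles after | 336 | 1 − exp(−0.230) = 20.5% | 1 − exp(−0.460) = 36.9% |
| 24 cycles after | 672 | 1 − exp(−0.460) = 36.9% | 1 − exp(−0.920) = 60.1% |

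For a given rate the ordering depends only on which period is longer. For a subject who completes 18 cycles, it reverses when later time exceeds 16.56 months.

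**3. Who reaches Cycle 19 at the CSR cut.** With a cut 6 months after the last first dose, nobody has reached Cycle 19 if accrual took 16.56 − 6 ≈ 10.5 months or less. The documents do not state accrual duration. Assume uniform accrual and exponential time on treatment with a 36-month median. The probability of still being on treatment at 16.56 months is then 2^(−16.56/36) = 0.727.

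- 12-month accrual: (18 − 16.56)/12 × 0.727 ≈ 9% of ELd, about 3 to 4 of 40.
- 18-month accrual: (24 − 16.56)/18 × 0.727 ≈ 30%, about 12 of 40.

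**4. Expected table entries.** These come from a simulation of 400,000 subjects with the step 3 assumptions, a constant 25 events per 100 person-years and the 60-day AE window. The cut is in months after the last first dose. The first-period percentage is of all ELd subjects.

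| Accrual, cut | Before | After, of those reaching Cycle 19 | After, of all ELd |
|---|---|---|---|
| 12 months, 6 | 20.1% | 1.5% | 0.1% |
| 18 months, 6 | 22.1% | 7.2% | 2.2% |
| 12 months, 24 | 26.1% | 22.1% | 16.1% |
| 12 months, 36 | 26.1% | 34.3% | 24.9% |
| 12 months, 48 | 26.2% | 41.7% | 30.3% |

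The true rate is the same in both periods throughout. The sign changes with the cut-off, and at 36 months it also depends on the denominator. The simulation makes stopping treatment independent of AE risk, so selection of subjects who tolerate treatment would come on top and is not quantified here.

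**5. The same data as rates.** With person-time divided at Cycle 19 Day 1, a constant rate gives an expected rate ratio of 1.0 at every cut-off.

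**The case against.** The strongest reply is that this is one descriptive bullet, with no test and no conclusion attached. The SAP never calls it an assessment of the 20 mg/kg schedule. That the table holds crude percentages is inferred from the word frequency and the default counting rule. Related information is planned elsewhere: the number of subjects taking each drug in each cycle (SAP 7.4.1.1), infusion reactions by cycle (SAP 7.6.3), exposure-adjusted rates by arm and a full AE listing (SAP 7.6.1). At a six-month cut the later column may be so sparse that nobody would rely on it. All of this stands and limits the weight of the point. None of it supplies period-specific person-time or a denominator.

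A reader might infer that the table will always make the 20 mg/kg period look safer. The documents do not support that. It follows only while later follow-up is shorter than the first period. Protocol 8.3.2.2 expects longer follow-up, under which the artefact can reverse.

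A reader might also infer that Cycle 19 has no place in either column. SAP 6.1 already treats Cycle 19 onward as its own on-treatment phase, so this is loose wording. A one-line definition is still useful, because the delay and omission rules in SAP 7.4.1.2 group Cycle 19 differently.

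**Conclusion.** The point holds as a two-directional problem. As written, the table compares up to 504 days in all treated ELd subjects with an unspecified remainder in those who continued, and no planned analysis adjusts for that by period. At a cut near six months after the last first dose, an unchanged rate would favour the later period strongly (20% to 22% against 1.5% to 7% of those reaching Cycle 19, for accrual of 12 to 18 months). With 48 months' follow-up it would count against it (26% against 42%). The figures rest on assumed accrual, time on treatment and a constant event rate. The dependence on cut-off needs only the unequal period lengths.

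The consequence is confined to the interpretation of a supplementary safety table. It should be corrected, but it does not touch the primary ORR analysis.

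**What to change.** In SAP 7.6.1:

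- Define the periods as first dose to the day before Cycle 19 Day 1, and Cycle 19 Day 1 onward. Protocol 4.5.3 fixes cycle starts relative to Cycle 1 Day 1, so the split date is known for every subject.
- Report events per 100 person-years in each period, assigning events by onset date. The existing formula cannot be reused unchanged. First-period person-time must end at the split for subjects who continue past it, and the 60-day tail should attach only to each subject's last period.
- Give the first-period rate for all treated ELd subjects and also for those who received elotuzumab in Cycle 19 or later. Give the later rate for that second group. Both first-period rates are needed: restricting to those who continued removes earlier treatment-ending AEs. The group must be defined by elotuzumab because Protocol 4.5.3 lets subjects stay on study therapy without it.
- State the denominators and keep the crude counts alongside.
- Footnote that selection remains and that the Day 15 AE assessment is not required from Cycle 19.

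The cost is modest programming on dates already collected, and imprecise later-period rates. In the 18-month accrual case, about 12 subjects with a mean of 3.6 months give 12 × 3.6/12 = 3.6 person-years, or 0.9 expected events at 25 per 100 person-years. That imprecision is real, and the revised table would make it visible.

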3.6.2 Lost to Follow-Up

All reasonable efforts must be made to locate subjects to determine and report their ongoing status. This includes follow-up with persons authorized by the subject as noted above. Lost to follow-up is defined by the inability to reach the subject after a minimum of three documented phone calls, faxes, or emails as well as lack of response by subject to one registered mail letter. All attempts should be documented in the subject's medical records. If it is determined that the subject has died, the site will use permissible local methods to obtain the date and cause of death.

If investigator's use of third-party representative to assist in the follow-up portion of the study has been included in the subject's informed consent, then the investigator may use a Sponsor-retained third-party representative to assist site staff with obtaining subject's contact information or other public vital status data necessary to complete the follow-up portion of the study. The site staff and representative will consult publicly available sources, such as public health registries and databases, in order to obtain updated contact information. If after all attempts, the subject remains lost to follow-up, then the last known alive date as determined by the investigator should be reported and documented in the subject's medical records.

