4.5.3 Dose Delay or Interruption

If the dose of one drug in the regimen (ie, lenalidomide, dexamethasone or elotuzumab) is delayed or interrupted, the treatment with the other drugs may continue as scheduled. Subjects experiencing a 28-day delay in all study drugs lenalidomide, dexamethasone, and elotuzumab due to an adverse event(s) related to study treatment must be discontinued from study drug. Subjects experiencing delays unrelated to study therapy, for example due to radiation therapy may delay study treatment up to 42 days. Delays greater than 28 days must be discussed with the medical monitor.

Each cycle is 28 days. While dose delays or interruptions are permitted, the start of each cycle cannot be delayed and is fixed relative to Cycle 1 Day 1. Adjustments to the Cycle 1 Day 1 anchored schedule should not be performed. Missed doses should be skipped, not delayed, if not given within the allowed window.

Subjects may continue on study therapy even if components of the study therapy must be discontinued. For example, a subject on lenalidomide and dexamethasone may continue on study therapy even if dexamethasone must be discontinued for an adverse event. Likewise, a subject on

the investigational arm may continue on study therapy if elotuzumab must be discontinued for an adverse event or other reason. Patients are considered still on study therapy even if they continue solely on lenalidomide.

Please consult the BMS medical monitor or any questions regarding dose interruption or study therapy discontinuation.

4.5.3.1 *Elotuzumab*

In Cycle 1 and 2, an elotuzumab dose that falls outside of the pre-specified window (-1 to +3 days) must be skipped.

In Cycles 3 and beyond, elotuzumab dosing may be delayed for up to 1 week. If unable to administer within 1 week, then the dose should be skipped and resumption of the elotuzumab continues per the protocol defined schedule.

4.5.3.2 *Dexamethasone*

Dexamethasone delay should be performed as clinically indicated at the discretion of the investigator.

For subjects receiving elotuzumab, the weekly dexamethasone dose that coincides with or is temporally closest to the elotuzumab dosing must be administered as part of the premedication for elotuzumab per the guidance in [Section 4.5.1](#).

4.5.3.3 *Lenalidomide*

Lenalidomide delay should be performed as clinically indicated at the discretion of the investigator.

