Dispense Study Drug	X	Those supplied by BMS or sourced by the investigator

Table 5.1-2: Short-term Procedural Outline (CA204116) Cycles 1 & 2

Procedure	Day 1	Day 8	Day 15	Day 22	Rest Days 23 - 28 ^a	Notes
Safety Assessments						
Targeted Physical Examination	X					Perform up to 3 days prior to dosing, include weight (Section 5.4.1)
Vital Signs	X	X	X	X		Measure vital signs prior to pre-medication, pre-elotuzumab infusion, 30 minutes after the start of elotuzumab infusion, at the end of infusion, and 30 and 120 minutes after the completion of infusion. Control arm measure vital signs once at each visit.
Performance Status (ECOG)	X					Evaluate prior to dosing
Serious Adverse Event Assessment	X	X	X	X		Evaluate prior to dosing
Adverse Events Assessment	X	X	X	X		Evaluate prior to dosing
Second Primary Malignancy	X					Section 6.7
Concomitant Medications	X	X	X	X		Evaluate prior to dosing
Laboratory Test for Safety						
CBC, differential, platelets	X	X	X	X		Can be drawn up to 3 days prior to study visit. (Section 5.4.4)
Serum Chemistry	X					Can be drawn up to 3 days prior to study visit. (Section 5.4.4) Serum calcium and albumin every 4 weeks from date of first dose of study drug until disease progression, even if subject is on subsequent therapy
Pregnancy Test	X	X	X	X		For WOCBP only. Urine tests must have a sensitivity of at least 25 IU/L. Weekly test within 24 hours of study medication.

Table 5.1-2: Short-term Procedural Outline (CA204116) Cycles 1 & 2

Procedure	Day 1	Day 8	Day 15	Day 22	Rest Days 23 - 28 ^a	Notes
Efficacy Assessments						

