8.3.2.2 Progression-Free Survival

The primary definition of Progression-free survival (PFS) is the time from randomization to the date of the first documented tumor progression, as determined by the investigator using the IMWG criteria, or to death due to any cause, provided death does not occur more than 10 weeks (2 or more assessment visits) after the last tumor assessment. Clinical deterioration will not be considered progression.

The following censoring rules will be applied for PFS:

- Subjects who receive systemic secondary anti-myeloma therapy prior to documented progression will be censored on the date of the last tumor assessment prior to the initiation of the new therapy.
- Subjects who have an event (documented progression or death) > 10 weeks (2 assessment visits) after the last prior tumor assessment will be censored at the last prior assessment.

- Subjects who do not progress and who do not receive subsequent therapy will be censored at their last tumor assessment.
- PFS also will be analyzed applying an intent-to-treat (ITT) definition that utilizes all data on each randomly assigned subject until either a progression event or the end of the study. PFS under the ITT definition will be defined as the time from randomization to the date of the first documented tumor progression or to death due to any cause. Clinical deterioration will not be considered progression. Subjects who neither progress nor die will be censored on the date of their last tumor assessment. There will be no censoring for subsequent therapy prior to progression or for progression events following missing assessments.

PFS is elevated from an exploratory endpoint to a secondary endpoint in the protocol amendment 03. The study duration is expanded, and PFS is expected to be sufficiently mature at the updated targeted follow-up, which is the time of final PFS analysis for the randomized global phase 3 study for the subjects with previously untreated multiple myeloma.

[REDACTED]

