8.5 Interim Analyses

The primary analysis will be done 6 months after last subject's first treatment. Additional analyses may be performed which depend on the timing of regulatory authority filing. The final analysis may be performed at the timing of the study discontinuation.

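### The exposure-adjusted AE rate, as printed, adds 60 days after last dose for every subject with no cap at death, loss or data cut-off, so it is understated

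*SAP*

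**What the plan says.** SAP 7.6.1 plans exposure-adjusted incidence rates per 100 person-years, by arm, for each system organ class and preferred term, counting repeat events. The denominator is the date of last dose minus "subject date of first dose of study drug} + 60 + 1" days, divided by 365.25. On-study AEs, the source of the numerator, are those "with an onset date on or after the first dose until 60 days after the last dose". The rate has a companion figure: it "and will be displayed along with a count of events".

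No minimum with date of death, last contact or data cut-off is printed in 7.6.1, and SAP 8.1 to 8.4 (baseline, age, duration and date conventions) add none. SAP 8.5 refers the handling of safety data to a sponsor convention that is not among the documents.

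On timing, Protocol 8.5 says "The primary analysis will be done 6 months after last" subject's first treatment; the SAP's Schedule of Analyses makes this a minimum. Protocol 8.3.2.2 records a later extension: "The study duration is expanded, and PFS is expected to be sufficiently mature at the updated targeted follow-up".

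**The concern.** The two windows agree only for a subject who was observed for all 60 days after last dose. For anyone else, days enter the denominator in which no event can enter the numerator, so the error runs in one direction.

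The plan itself expects such subjects. Treatment is open-ended (SAP 2.1 and 6.2), the disposition table counts subjects still on treatment (SAP 7.3.1), and deaths within 60 days of stopping are tabulated (SAP 7.6.5). The Day 30 and Day 60 post-treatment AE assessments in Protocol Table 5.1-3 cannot have happened for a subject still on drug at cut-off.

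At stake is a prespecified safety output in a study whose results are meant to support the Japanese submission together with the global trial (SAP 5). Event rates would be reported as lower than the observed data show.

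**Working it through.** The documents state no rate or person-time total, so there is no figure to reproduce. The check evaluates the printed formula.

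**One ongoing subject.** Let F be the days from first dose to cut-off and g the days from last dose to cut-off. Printed days = F − g + 61. Observed days = F + 1. Understatement = 1 − (F + 1)/(F − g + 61) = (60 − g)/(F − g + 61). Six months is taken as 183 days.

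| g | F = 183 | F = 365 | F = 730 |
|---|---|---|---|
| 0 | 60/244 = 24.6% | 60/426 = 14.1% | 60/791 = 7.6% |
| 7 | 53/237 = 22.4% | | |
| 28 | 32/216 = 14.8% | 32/398 = 8.0% | 32/763 = 4.2% |
| 42 | 18/202 = 8.9% | | |

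The gaps come from the Protocol:
- Seven days arises without any hold. The schedule has "Rest Days 23 - 28", and the last dose can fall on Day 21 (lenalidomide alone, or dexamethasone given a day early), with cut-off on Day 28.
- Twenty-eight days is the hold in Protocol 4.5.3 ("Subjects experiencing a 28-day delay in all study drugs").
- Forty-two days is the limit in the same section for delays unrelated to study therapy.

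**Death 30 days after last dose**, d days from first to last dose: 30/(d + 61), which is 30/244 = 12.3% at d = 183 and 30/426 = 7.0% at d = 365. **Full 60 days observed:** 0%.

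**One arm at the earliest cut.** The documents do not give accrual time, the share ongoing or the stopping time, so these are assumptions. Take uniform accrual over 12 months, so F runs from 183 to 548 days with mean 365.5. A share f is ongoing with g = 0. The rest stop at F/2, so each has at least 91 days of observation after last dose and a complete 60-day window.

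Mean printed days = f(365.5 + 61) + (1 − f)(182.75 + 61). Mean excess = 60f.

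- f = 0.4: 24/316.9 = 7.6%
- f = 0.6: 36/353.4 = 10.2%
- f = 0.8: 48/390.0 = 12.3%

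For 40 subjects the excess is 40 × 36/365.25 = 3.9 of 38.7 person-years at f = 0.6, and 5.3 of 42.7 at f = 0.8. Deaths and losses are not in this model and would add to it.

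**Sensitivity.**
- Accrual of 6 to 18 months: 12.8% to 8.4% at f = 0.6, and 15.6% to 10.2% at f = 0.8.
- Stopping at 25% or 75% of follow-up, with 12-month accrual: 11.4% or 9.4% at f = 0.6, and 12.9% or 11.8% at f = 0.8.
- Cut 730 days after the last first dose, with 12-month accrual (mean F = 912.5): 36/791.0 = 4.6% at f = 0.6, and 48/882.3 = 5.4% at f = 0.8.

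**Between arms.** If one arm has 80% ongoing and the other 60%, the rate ratio is multiplied by 0.877/0.898 = 0.976 at the earliest cut (0.968 to 0.981 over 6 to 18 months' accrual). At the 24-month cut it is multiplied by 0.991.

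**The case against.** The strongest reply is that little depends on this rate. It is descriptive, event counts stand beside it, no test or decision rule uses it, and SAP 5 plans no formal comparison between arms. All of that stands, and it limits the weight of the point. It does not make the printed formula right: applied as written, it gives a wrong number, not merely an incomplete description.

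A second reply is that the cap may already exist in the sponsor convention cited in SAP 8.5. That is possible. SAP 7.6.1 sends the reader to Section 8.4 for imputing AE onset dates, and 8.4 has no such rule, which suggests that some AE conventions sit outside the SAP. The point is therefore confined to the formula as printed.

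Third, the arm-level size rests on assumed accrual, stopping times and shares ongoing. That is true, so ranges are given. The direction does not depend on them.

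Some stronger readings are tempting, but the documents do not support them:
- A reader might infer that adding 60 days is itself the mistake. It mirrors the AE window and is correct for a fully observed subject.
- The formula shows one subject's dates under an arm-level count, and a reader might call the missing sum an error. It is more likely shorthand or loss in text extraction.
- The dose-intensity formulas in SAP 7.4.1.3 use the date of death, and a reader might cite them as precedent for a cap at cut-off. They contain no cut-off term.

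**Conclusion.** The point holds for the formula as printed. Person-time is overstated and the rate understated for subjects on treatment or less than 60 days off it at cut-off, and for those who die or are lost within 60 days of last dose.

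The arm-level size is about 8% to 12% at the earliest analysis with 40% to 80% ongoing, and about 5% at a cut 24 months after the last first dose with 60% to 80% ongoing. Both rest on 12-month uniform accrual and discontinuers stopping halfway. The 24.6% figure belongs to a single subject at 183 days with last dose at cut-off; it should not be read as the error in an arm's rate.

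A reader might also infer that the comparison of arms is seriously biased, or biased towards elotuzumab. The documents do not show this: the ratio moves by about 2% in the worked case, and they do not say which arm will have more subjects ongoing. Worst-grade AE tables, SAE and death tables and all efficacy results are untouched. The correction is worth making because the bias is one-directional and easily avoided.

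**What to change.** In SAP 7.6.1, define an arm's person-time as the sum over treated subjects of [min(last dose + 60 days, date of death, data cut-off) − first dose + 1]/365.25.

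Only for subjects lost to follow-up or withdrawn from all follow-up within 60 days of last dose, also cap at the last visit or contact with an AE assessment, but never before the last dose. This cap should not apply to everyone. Scheduled AE assessments fall on Day 1 only from Cycle 19 (Protocol Table 5.1-3), while lenalidomide runs to Day 21 and dexamethasone to Day 22, so a general cap would discard time on drug.

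Do not use a last-known-alive date for the cap. Protocol 3.6.2 lets sites consult public sources, and if the subject stays lost, "then the last known alive date as determined by the investigator should be reported"; being known alive does not mean that AEs were assessed.

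Apply the same end date to the events counted in this rate, so that numerator and denominator cover one window. If the convention cited in SAP 8.5 already sets such a cap, state it in 7.6.1.

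The cost is a small change to the SAP and the program, using visit, dosing and death dates already collected. For lost subjects the last AE assessment must be derived from visit records. Reported AE rates will be somewhat higher.
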